3.4 Criteria for Withdrawal

The subjects are allowed to spontaneously discontinue participation in this study at any time. The investigator may discontinue participation of a subject in this study at any time as per the subject's decision. However, a subject who are terminated early for showing a sufficient level of efficacy of the investigational product will not be considered as a withdrawal. If a subject is withdrawn from the study, the study results obtained from the discontinued/withdrawal case until the time point of discontinuation/withdrawal may be reviewed for evaluable items at the final evaluation.

In following cases, the investigator may withdraw the subject from the study.

- 1) Violation of inclusion/exclusion criteria is identified during the study.
- 2) Subjects are considered difficult to continue with the study due to adverse events as per the investigator's decision.
- 3) Subjects have received or are deemed to require medications or treatments that may affect the study results during treatment period or follow-up period.
- 4) Voluntary consent withdrawal by the subject or subject's legally acceptable representatives.
- 5) Subjects cannot not cooperate with the investigator.
- 6) Lost to follow-up.
- 7) The investigator decides to withdraw subjects.
- 8) Subject is pregnant during the study

If a subject determines to discontinue his/her participation and withdrawn from the study prior to completion, procedures scheduled for the Withdrawal visit should be performed. The procedure for the Withdrawal visit will be conducted within 2 weeks after the withdrawal decision is made. At the Withdrawal visit, the unused IPs or empty packaging will be returned, and the subject diary will be collected.

If the patient refused to visit, the vital sign, physical examination and lab test can be exclude. However, assessment of Gastroesophageal Reflux Disease Questionnaire (GERD-Q) and quality of life questionnaire (GERD-HRQL) must be performed at least by telephone call by the investigator, and all document should be written on the EMR by the investigator.s. To prevent any missing AEs that the investigator is not aware of, all kinds of methods must be employed to directly contact the subjects who refuse to visit such as phone call, letter, or personal visit. Any withdrawn subject cannot participate in the same study again.

4 Description of Study Design

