
	
retrospective study] that doesn't affect this study's efficacy and safety as determined by the investigator.)
 
[Laboratory tests]
 
12) At screening, those who had
 
 ① serum alanine aminotransferase (ALT), aspartate aminotransferase (AST), or total bilirubin levels ≥ 2 X upper limit of normal ② serum creatinine or BUN ≥ 2 X upper limit of normal 
[Others]
 
13) Pregnant or breast-feeding women
 
14) Those who do not consent to use appropriate contraceptive methods during the study.
 
 - Appropriate contraceptive methods for patients or their partners - For Male subject: to use barrier method such as male condom and surgical sterilization such as vasectomy - For Female subject: to use 1) hormonal contraceptive such as Intrauterine system : intrauterine hormone-containing system, implant, injection, contraceptive pills, or 2) non hormonal contraceptive such as Intrauterine system : copper loop, barrier method : female condom, diaphragm or cervical cap, or surgical sterilization : tubectomy. 
15) In the opinion of the investigator, those who were unsuitable for any reason.

Investigational product and mode of administration	
[Investigational Product]
 
 ● Study drug: Fexuprazan tablet 40 mg ● Control drug: Esomeprazole capsule 40 mg 
[Treatment period]
 
 ● Treatment 1: 4 weeks A dose of Study drug or Control drug will be administered orally once daily without regard to meals for 4 weeks. The timing of administration should be kept consistent for each subject. ● Treatment 2: Up to 8 weeks (4 weeks + 4 weeks) Patients who have not been healed after the Treatment 1 of investigational product administration will have an additional 4-weeks of treatment period (Treatment 2) with the same mode of administration. Patients that categorized as a non-healed are those with a GERD-Q score >8.

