5.1 Scheduled Completion

If all protocol-specified procedures and assessments are completed after the IP administration, the subject will be considered to have completed the study. Subjects with symptoms relief at Week 4 measured by GERD-Q Score <8 will have the Safety F/U after 2 weeks from the date and be terminated from the study.

In this study, completion of the last subject is defined as the end of study.

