8.3.3 Questionnaire assessment

- Gastroesophageal Reflux Disease Questionnaires (GERD-Q) (See Appendix 3)
 - The subject will complete the GERD-Q at the screening visit (Visit 1) and Visit 2. The test results from Visit 1 will be used as the basis to determine eligibility for inclusion/exclusion.
 - The subjects who meet the inclusion criteria will complete the GERD-Q at Visit 3, Visit 4, and Visit 5.
- Quality of Life assessment (GERD-Health Related Quality of Life, GERD-HRQL) (See Appendix 4)
 - The subjects who meet the inclusion criteria will complete the GERD-HRQL questionnaire at Visit 2, Visit 3, Visit 4 and Visit 5.^[19, 20, 21]

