8.4 Efficacy Assessment

8.4.1 Efficacy Endpoints

8.4.1.1 Primary Efficacy Endpoint

Proportions of subjects with symptoms relief at week 4 measured by GERD-Q Score <8

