9.2.3 Efficacy Endpoints

9.2.3.1 Primary Efficacy Assessment

Proportions of subjects with symptoms relief at Week 4

The proportions of subjects with symptoms relief by Week 4 and their 95% confidence intervals will be provided by group.

The proportions of subjects with symptoms relief by Week 4 will be calculated as the cumulative symptoms relief by using the results at the time of final observation including the Withdrawal visit. To compare the control group and study group, the lower bound of the 2-sided 95% confidence intervals will be obtained by using Chi Square test or Fisher's Exact test method. If this lower bound is greater than the non-inferiority margin of -0.1, the study group will be judged to be non-inferior to the control group.

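### Section 3.4 leaves open an efficacy exit before Week 4, and 9.2.3.1 would then let a Day 7 GERD-Q count as Week 4 relief, clearly so in the FAS

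*Combined protocol and SAP*

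**What the plan says.** Section 3.4 (Criteria for Withdrawal) states that "a subject who are terminated early for showing a sufficient level of efficacy of the investigational product will not be considered as a withdrawal". It names no score, visit or assessor.

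Section 5.1 (Scheduled Completion) places the relief-based exit at one time: "Subjects with symptoms relief at Week 4 measured by GERD-Q Score <8 will have the Safety F/U after 2 weeks from the date". It also defines completion: "If all protocol-specified procedures and assessments are completed after the IP administration, the subject will be considered to have completed the study". The synopsis describes Treatment 1 as a full course: "A dose of Study drug or Control drug will be administered orally once daily without regard to meals for 4 weeks".

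The primary endpoint in 8.4.1.1 is "Proportions of subjects with symptoms relief at week 4 measured by GERD-Q Score <8". Section 9.2.3.1 analyses relief by Week 4, "calculated as the cumulative symptoms relief by using the results at the time of final observation including the Withdrawal visit". Under 8.3.3, enrolled subjects "will complete the GERD-Q at Visit 3, Visit 4, and Visit 5", which the schedule puts at Days 7, 28 and 56.

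Section 3.4 and footnote 12 of the table in 8.2 require a GERD-Q, by telephone if necessary, from subjects who discontinue or are withdrawn. Under 9.1 the FAS needs one dose and one efficacy result, and the PPS takes FAS subjects who complete the study without a major deviation. Section 9.2.1 makes the PPS the primary set.

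**The concern.** The trial asks whether relief after 4 weeks of fexuprazan is non-inferior to relief after 4 weeks of esomeprazole. Section 3.4 appears to recognise an exit for good response with no stated time or criterion, in an open-label trial. If that exit can happen before Visit 4, the subject has no Week 4 score and, not being a withdrawal, is not sent to the visit where a GERD-Q is mandatory. The final-observation rule would then fall back on the Visit 3 score. A subject relieved at Day 7 whose symptoms would have returned by Day 28 would be scored as a success. Enough such subjects, spread unevenly between arms, would distort the difference that is compared with the margin of -0.1.

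**Working it through.** **Step 1. Is an efficacy exit before Week 4 possible on the text?**

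- Pointing to Week 4 at the earliest: 5.1 sets the relief exit at Week 4; 7.1 and 8.1 determine healing only at Visits 4 and 5; 7.1 has another 3 weeks of drug prescribed at Visit 3.
- Leaving room for an earlier exit: 3.4 calls the termination early, whereas 5.1 treats the Week 4 exit as scheduled; 4.1 and 6.2 give 4 weeks as an upper limit; 7.1 times the safety follow-up from confirmation of healing, not from Visit 4.

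The text neither creates such an exit procedurally nor excludes it.

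**Step 2. Trace one subject: GERD-Q below 8 at Visit 3 (Day 7), drug then stopped for efficacy.**

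| Rule | Consequence |
|---|---|
| 3.4 | Not a withdrawal |
| 3.4 and 8.2 footnote 12 | No exit GERD-Q triggered |
| 9.1, FAS | Included: dosed, one efficacy result |
| 9.2.3.1 | Final observation is Day 7, so relieved by Week 4 |
| 8.4.1.1 | No observation at Week 4 |

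**Step 3. Compare an ordinary withdrawal at Day 7.** The Withdrawal visit falls within 2 weeks, so by Day 7 + 14 = 21. The Visit 4 window opens at Day 28 - 5 = 23. That subject also lacks a Week 4 score, but does give a second GERD-Q.

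**Step 4. Is the traced subject in the PPS?** Not all procedures in 5.1 were done, so strictly the subject is not a completer and is out. Against that, 3.4 says the subject did not withdraw, and no passage settles which status governs. The compliance limit in 13.5 (below 80% is a major deviation) does not decide it, because 7.3.3 does not define the doses due in a shortened course: 7/28 = 25% against the full course (out), 7/7 = 100% against doses due up to the stop (in).

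**Step 5. Scale.** The plan's sample size first. With rates 0.94 and 0.885, margin 0.10 and n = 53:

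- SE(pooled) = sqrt(2 x 0.9125 x 0.0875 / 53) = 0.0549
- SE(unpooled) = sqrt((0.94 x 0.06 + 0.885 x 0.115) / 53) = 0.0546
- Power = Phi((0.155 - 1.96 x 0.0549) / 0.0546) = 0.807, matching the stated 0.80729
- 53 / 0.8 = 66.25, so 67 per arm and 134 in total, as stated

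The point does not touch that arithmetic. One reclassified subject moves an arm's rate by 1/67 = 1.5 points or 1/53 = 1.9 points.

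The shift in the observed difference is f_T x r_T - f_C x r_C, where f is the share of an arm stopped early for efficacy and r the share of those who would not be relieved at Week 4. The documents give none of these four values.

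As a sensitivity range only, suppose the true rates lie at the margin (78.5% against 88.5%) and a net 0 to 8 points of unrelieved subjects is scored as relieved in the fexuprazan arm. Exact binomial enumeration, with a 95% Wald interval as my assumption, gives this chance of a false non-inferiority claim:

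| Assumed net shift (points) | 0 | 2 | 4 | 6 | 8 |
|---|---|---|---|---|---|
| n = 53 per arm | 3.1% | 5.7% | 9.9% | 16.6% | 26.1% |
| n = 67 per arm | 3.0% | 5.9% | 10.9% | 19.0% | 30.9% |

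The excess over 2.5% at zero shift comes from the Wald interval, not from early stopping. A net shift in the control arm would act the other way.

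**The case against.** The ordinary reading of 3.4 may remove the problem. Section 5.1 also describes subjects relieved at Week 4 as terminated from the study. Against the 8-week maximum in 7.2.2, a Week 4 exit is early, so the clause may only prevent those subjects being counted as dropouts. Efficacy is not among the numbered withdrawal reasons in 3.4. This reading is reasonable and may be what was meant. What stands is that the clause does not state it.

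Second, the scoring rule, not the withdrawal label, produces the success: Step 3 shows that any exit around Day 7 is scored without a Week 4 observation. This is correct, and it is why the analysis fix belongs in 9.2.3.1 and covers every reason for stopping. The label's own effect is to remove the exit GERD-Q.

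A reader might infer more in two respects, and the documents support neither.

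- That an efficacy stop is itself a success in the primary analysis. No section says so. A post-baseline GERD-Q below 8 is still needed, and on the strict reading of 5.1 and 9.1 the subject is not in the PPS.
- That early stops would be more frequent on fexuprazan and push the result towards non-inferiority. Sections 1.4 and 1.6 report faster symptom relief in phase 2. However, the nearest figure, subjects free of major symptoms for 7 days (21.57% against 12.50%), was not significantly different, came from erosive disease, and is not a rate of stopping drug.

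**Conclusion.** The point holds as an inconsistency and a scoring gap. Section 3.4 describes an efficacy termination without a criterion or time, 5.1 places relief-based exit at Week 4, and the by-Week-4 rule in 9.2.3.1 can satisfy an at-Week-4 endpoint with a Day 7 score. The consequence is clear for the FAS. For the PPS, the strict reading excludes the subject, but the plan does not say that it governs.

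This rests on one condition: that a subject actually stops before Visit 4 on the 3.4 ground. If the clause covers only Week 4 exits, a clarifying phrase settles that part, and the final-observation rule remains open for other early exits. The documents give no basis for the size or direction of a bias. The table in the working shows sensitivity to assumed shifts and is not an estimate.

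**What to change.** Reconcile 3.4 with 5.1, 7.1, footnote 12 of 8.2, 9.1 and 9.2.3.1. The sponsor should state whether an efficacy exit before Week 4 exists. Which stopping rule applies is for the sponsor to decide.

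Whatever the answer, add to 9.2.3.1 that any subject whose drug stops before Visit 4, for any reason:

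- is asked for a GERD-Q at the planned Day 28 contact, by telephone if needed, as is already allowed for withdrawals;
- is not a PPS completer;
- is not counted as relieved at Week 4 on a Day 7 or other pre-window score.

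The cost is a few sentences, a few telephone questionnaires and possibly a slightly lower relief rate.

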4.1 Study Period

- Study duration: Approximately 14 months from IRB approval to completion
- Study duration for each subject: 8-12 weeks
 - Screening period: Up to 2 weeks
 - Treatment period: Up to 4 weeks (unhealed subject will continue additional 4 weeks of treatment)
 - Follow-up period: For 2 weeks from the last dose

4.2 Study Design

A Multi-Center, Randomized, Open label, Double-arm, Controlled study, Investigator Initiated Trial.

4.3 Rationale for Study Design

4.3.1 Rationale for Establishment of Efficacy Endpoints

The clinical study guidelines for gastroesophageal reflux disease treatments requires 4 to 8 weeks of treatment period in general. In Indonesian guideline, Gastroesophageal Reflux Disease (GERD) is diagnosed by GERD Q score > 7 , so the proportion of subject with symptom relief indicator is indicated by GERD-Q < 8 ^[7,12,13]

Also, typical symptoms of gastroesophageal reflux disease are heartburn and acid regurgitation and the clinical study guidelines for gastroesophageal reflux disease treatments specifies to include endpoints for evaluating disappearance of such symptoms. ^[12] Assessment on symptoms includes severity and frequency and, since symptom assessment by physicians or investigators is less reliable, the subjects have to assess their symptoms by themselves.^[12] Given that, this study sets the assessment on symptoms based on the diary of subjects as a secondary efficacy endpoint.

4.3.2 Rationale of Establishment of Treatment Period

In accordance with the clinical study guideline for gastroesophageal reflux disease treatments, 4 to 8 weeks of treatment period is generally recommended in a clinical study on gastroesophageal reflux disease ^[12,13] and this study set 4 weeks of Protocol No.DW_DWP1401262001

dosing period in consideration of dosing periods in other clinical studies on gastroesophageal reflux disease.^[14,15,16]

4.3.3 Rationale of the Dosing Interval

In a phase 1 clinical study performed in Korea, the elimination half-life in blood of Fexuprazan was 9 hours and acid secretion suppression were maintained until the nighttime with once-daily dosing. Also, in the phase 2 study conducted in patients with erosive gastroesophageal reflux disease, Fexuprazan 40 mg was administered once daily for up to 8 weeks, and it was effective in endoscopic healing and alleviating the symptoms. Especially, the symptoms were improved faster than the active control, Esomeprazole 40 mg group, and the nighttime symptoms were also improved effectively. Therefore, the dosing interval of Fexuprazan was set with once-daily dosing as with the active control.

4.4 Randomization Method

This clinical study is an open label trial. The randomization list will be prepared by an independent party from PT Equilab International and reviewed by PT Equilab International's consultant. The investigational product (IP) will be dispensed by an independent party who has qualification as pharmacist prior to dosing day. The site study pharmacist will administer the dispensed IP to the subjects based on the randomization. The randomization will be balanced and the randomization code will be kept under controlled access. If a subject provides a written consent to participate in this clinical study, screening number will be assigned, and subjects who meet all the inclusion criteria and none of the exclusion criteria based on the screening test results will be assigned to randomization numbers and randomized in a 1:1 ratio to one of study group or control group.

The randomization number will be denoted by for example, '00RXXX' (ex.01R001) and means the following.

- '00': means site number.
 - 01: RS. University of Indonesia
 - 02: RS. Islam Cempaka Putih
 - 03: RS. MMA
- 'R': means randomization.
- 'XXX': order of randomized subjects

5 Criteria for Completion and Early Termination of Study

5.1 Scheduled Completion

If all protocol-specified procedures and assessments are completed after the IP administration, the subject will be considered to have completed the study. Subjects with symptoms relief at Week 4 measured by GERD-Q Score <8 will have the Safety F/U after 2 weeks from the date and be terminated from the study.

In this study, completion of the last subject is defined as the end of study.

5.2 Early Termination

The sponsor may terminate the study early in overall or at specific study sites. Reasons for termination of the study by the sponsor are as follows:

- 1) Failure to meet expected enrollment goals in overall or at specific study sites.
- 2) Emergence of any efficacy/safety information that may significantly affect continuation of the study.
- 3) Violation of Good Clinical Practice (GCP), the protocol, or the contract by a study site or the investigator, disturbing the appropriate conduct of the study.
- 4) Any other administrative reasons that may affect continuation of the study.

The investigator and Institutional Review Board may terminate the study when they determine that the benefits that individuals and the society may gain do not outweigh or justify the risks and discomforts, based on information observed and collected during the study.

6 Identity and Management of Investigational Products

6.1 Investigational Products

6.1.1 Study Drug

The investigational product Fexuprazan is a green, oval-shaped film-coated tablet. Drug substance and content for each tablet are as follows:

- 1) Code Name: Fexuprazan
- 2) Dosage form and appearance: green, oval-shaped film-coated tablet
- 3) Drug substances and their contents:

Compounding purpose	Ingredient name/Weight	Specification	Content
---------------------	------------------------	---------------	---------

Active ingredient	FEXUPRAZAN/624 mg	Self-specification	40.00 mg
-------------------	-------------------	--------------------	----------

4) Storage condition: Store in a tight container at room temperature (1–30°C)

6.1.2 Control drug

Commercially available esomeprazole, as a treatment for gastroesophageal reflux disease, is selected as the control drug for this study and its product name, content, dosage form, etc. are as follows:

- 1) Product name (Ingredient name): ESOFERR (Esomeprazole 40mg)
- 2) Dosage form and appearance: Hard gelatin capsule, Buff opaque with Dexa logo (black), contain off-white to greyish pellets
- 3) Drug substances and their contents:

Compounding purpose	Ingredient name	Content
Active ingredient	Esomeprazole	40 mg

4) Storage condition: Store in a tight container at room temperature (1–30°C)

6.2 Administration Route and Method of Investigational Products

For maximum 4 weeks from the next day of investigational product prescription, 1 tablet/capsule will be administered orally once daily without regard to meals. Tablets/capsules should be taken at a regular time, if possible.

6.3 Labeling and Packing of Investigational Product

The investigational products (IPs) will be manufactured and packaged by Daewoong Pharmaceutical Co., Ltd, a South Korean Pharmaceutical company located at [name], and then imported to the assigned Clinical Research Organization – PT. Equilab International which office is located at [name] and delivery to the clinical trial pharmacists at each of the study sites.

For IP labeling, the following information is labeled on the packaging of the IP, as detailed in Indonesian Food and Drug Authority Regulation:

- 1) A statement that it can only be used for the purpose of clinical study (e.g., “For clinical use only”).
- 2) Investigational product name or identification mark (state study drug and control drug for open label study).
- 3) Batch number for identifying contents and packaging job.
- 4) Protocol Number.
- 5) Quantity of dosage units.
- 6) Dispense date or visit number.
- 7) Subject number and initials.
- 8) Route of administration.
- 9) Additional information: Storage condition, expire date, etc.

6.4 Dispensing, Storage, Accountability and Recording of Investigational Product

The assigned CRO will deliver the IPs to the principal investigator or clinical trial pharmacist designated by the principal investigator of each study site. The clinical trial pharmacist should be aware of any receipt, volume of shipment, and condition of IPs and retain records of receipt, dispensing, and return of the IPs.

6.4.1 Dispensing

Dispensing of any products used for the study should be done based on the prescription signed by the principal investigator or sub-investigators who are participating in this study.

6.4.2 Storage Conditions and Accountability

The principal investigator and clinical trial pharmacist of study site are responsible for managing the IPs.

The assigned CRO will deliver the IPs to the clinical trial pharmacist, and the clinical trial pharmacist is in charge for receipt, inventory control, subject-by-subject dispensing, and return of the IPs, record relevant details, and inform relevant information to the principal investigator periodically.

The clinical trial pharmacist or the principal investigator or sub-investigator who controls IPs will record the date of dispensing, quantity, batch or serial number, and expiry or use-by date of IPs, IP number and randomization number (or screening number) for each subject in the drug accountability logs, and store and maintain them. The clinical trial pharmacist should complete dosing records to confirm each subject has received appropriate dosage specified in the protocol and should verify that IP inventory matches documented inventory.

The principal investigator should ensure that IPs are administered and managed in accordance with the protocol.

The IPs will be stored under storage conditions (room temperature, tight container) as determined by the manufacturer in a secure, limited-access storage area. In case any concern about the quality of the IPs is suspected or raised, the IPs should not be administered, and the sponsor should be notified promptly.

The study monitor will periodically access the management records to check the history of IP use and storage status. The investigator must not use the IPs and relevant materials for any purpose other than protocol specifics.

